#### **6.2.5.1. Cardiovascular hospitalizations, ED and unscheduled office visits**

##### **6.2.5.1.1. Hypothesis**

The following hypothesis will be tested.

$$H_0: \theta_{\text{cryo}} = \theta_{\text{AAD}}$$

$$H_a: \theta_{\text{cryo}} \neq \theta_{\text{AAD}}$$

where  $\theta_{\text{cryo}}$  and  $\theta_{\text{AAD}}$  are the 12-month rates of cardiovascular HCU events in the cryoballoon ablation and AAD arms, respectively.

##### **6.2.5.1.2. Endpoint Definition**

Healthcare utilization (HCU) events for this objective are defined as cardiovascular-related hospitalizations, cardiovascular-related emergency department visits, or cardiovascular-related unscheduled office visits occurring within 12 months after the index ablation (cryo arm) or the initiation of therapy (AAD arm). Events occurring >365 days after initiation of treatment but before the 12-month visit (if within its window) will be included.

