11.5.3.8. Cardioversion

- a. Electrical or pharmacological cardioversion to sinus rhythm must be attempted following the PVI portion of the procedure if sinus rhythm wasn't restored. Cardioversion may be performed prior to PVI if needed.

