15.3.3.5. Rationale for Performance Requirements

If the test specified above indicates a statistically significant increase in the time to the first HCU event between cryoballoon ablation and AAD-treated subjects, this is sufficient evidence to say that the treatment has a lower rate of healthcare utilization within a year of treatment initiation, due to the randomized and intention-to-treat nature of the comparison.

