### **6.2.4. Secondary Objective 1: Quality of Life**

Assess changes in quality of life between baseline and 12 months in the cryoballoon ablation arm.

There are two hypotheses tested in the objective, with separate hypothesis tests for (1) the difference in composite scores from the AFEQT questionnaire taken at baseline and 12 month visits, and (2) for the difference in composite scores for the EQ-5D questionnaire taken at baseline and 12-month visits. Hypothesis tests for this objective and secondary objective 2 will have type I error controlled using the Hochberg procedure, which is described in section 6.5. Testing for secondary objectives will only be performed if the primary objectives are met.

Comparison to the AAD arm is not planned as it is expected that a large percentage of AAD arm subjects will have a cryoballoon procedure during the 12 months of follow-up. An intention-to-treat comparison between the treatment and control arms would be biased toward the null hypothesis of no difference in such circumstances.

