##### **6.2.5.1.3. Analysis Methods**

The probability of a subject achieving freedom from HCU events (defined above) at 12 months will be estimated using Kaplan-Meier survival analysis. The standard error will be approximated using Greenwood's formula. A two-sided 95% log-log confidence interval for the probability at 12 months will be constructed. A two-sided log rank test will be used to assess whether the HCU event rate differs between treatment groups. If the p-value from this log-rank test is less than the alpha level determined by the Hochberg procedure (described in section 6.5), the objective will be considered met.

Day 0 is defined as day of the index cryoablation procedure or the day in which drug therapy is initiated. For subjects with treatment failure, the survival date will be set to the date of the first HCU event. For subjects without any HCU events through 12 months, those subjects will be censored at the last study contact date recorded on a CRF which may include the last study visit, the exit date or the date of death. If a subject without any HCU events is lost to follow-up, the censoring date will be set to the last known study visit date. For HCU events occurring on the day of index treatment, survival time will be set to 0.5 days.

The survival curve from 0 to 12 months will be presented for both treatment arms. HCU events will also be summarized by type and treatment group.

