#### **6.2.5.2.2. Endpoint Definition**

A cardioversion event is defined as an electrical or pharmacological cardioversion post index ablation discharge for the treatment arm, and post AAD initiation for the AAD arm.

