#### **6.2.5.2.3. Analysis Methods**

The probability of a subject achieving freedom from cardioversion (defined above) at 12 months (365 days) will be estimated using Kaplan-Meier survival analysis. The standard error will be approximated using Greenwood's formula. A two-sided 95% log-log confidence interval for the probability at 12 months will be constructed. A two-sided log rank test will be used to assess whether the cardioversion rate differs between treatment groups. If the p-value from the log-rank test is less than the alpha level determined by the Hochberg procedure (described in section 6.5), the objective will be considered met.

Day 0 is defined as the day of the index cryoablation procedure or the day in which drug therapy is initiated. For subjects with at least one cardioversion, the survival date will be set to the date of the first cardioversion. For subjects without any cardioversions through 12 months, those subjects will be censored at the last study contact date recorded on a CRF which may include the last study visit, the exit

date, or the date of death. If a subject without any cardioversions is lost to follow-up, the censoring date will be set to the last known study visit date. For cardioversions occurring on the day of index treatment, survival time will be set to 0.5 days.

The survival curve from 0 to 12 months will be presented for both treatment arms. Counts of all cardioversions administered over 12 months will also be summarized.

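### The cardioversion endpoint treats ablation procedures differently by arm, and the health care utilization endpoint does not say which ablation stays count, so both between-arm secondary tests can be biased

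*SAP*

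**What the plan says.** **Cardioversion.** SAP 6.2.5.2.2 defines an event as an "electrical or pharmacological cardioversion post index ablation discharge for the treatment arm, and post AAD initiation for the AAD arm". SAP 6.2.5.2.3 then adds: "For cardioversions occurring on the day of index treatment, survival time will be set to 0.5 days". Protocol 11.5.3.8 says "Electrical or pharmacological cardioversion to sinus rhythm must be attempted following the PVI portion of the procedure", on the condition that sinus rhythm has not already returned. Protocol 11.5.10 collects cardioversion use at repeat and crossover ablations.

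**HCU.** SAP 6.2.5.1.2 counts cardiovascular hospitalizations, emergency visits and unscheduled office visits "occurring within 12 months after the index ablation (cryo arm) or the initiation of therapy (AAD arm". SAP 6.2.5.1.3 adds: "For HCU events occurring on the day of index treatment, survival time will be set to 0.5 days". Neither section mentions index, repeat or crossover ablation stays.

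**Analysis.** Both endpoints are compared in the mITT cohort as randomized, by a two-sided log-rank test on time to first event, with no censoring at crossover. They are two of the four hypotheses under the Hochberg procedure (SAP 6.5), tested only if the primary objectives are met.

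**Crossover.** In explaining why quality of life is not compared between arms, SAP 6.2.4 says "it is expected that a large percentage of AAD arm subjects will have a cryoballoon procedure during the 12 months of follow-up". Protocol 11.5.2 allows crossover only after AAD treatment failure.

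**Claim.** Protocol 15.3.3.5 says of a significant HCU result that "this is sufficient evidence to say that the treatment has a lower rate of healthcare utilization within a year of treatment initiation". Protocol 15.3.4.5 says the equivalent for cardioversion.

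**The concern.** A between-arm test is interpretable only if the same occurrence is an event in both arms. For cardioversion it is not: one given before discharge from an ablation is ignored at the index procedure and counted at a crossover procedure. For HCU, the natural reading of the start of counting leaves out the cryo arm's index stay, while an AAD subject admitted for the same procedure later has an event.

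The plan drops the quality-of-life comparison because crossover would pull it toward no difference. It keeps these two comparisons, where crossover procedures can push the result toward cryo, and gives no handling rule. The gate does not protect against this. Meeting primary superiority implies more AAD failures than cryo failures, and failure is the condition for crossover. Two multiplicity-controlled hypotheses could therefore be met partly because control subjects received the study procedure later. Randomization and as-randomized analysis do not repair an endpoint that is defined differently by arm.

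A smaller point concerns wording. SAP 6.2.5 states the HCU hypothesis as a rate of total events, but the test concerns the first event only.

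**Working it through.** **1. The plan's own figure.** No power is stated for the HCU or cardioversion tests. The primary efficacy calculation supplies the failure rates used below, so it is reproduced first (SAP 7.1: 69.9% vs 45.9%, two-sided 0.05, 90% power):

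n per arm = [1.960·√(2·0.579·0.421) + 1.282·√(0.699·0.301 + 0.459·0.541)]² / 0.240² = (1.3685 + 0.8680)² / 0.0576 = 86.8, rounded up to 87. The total is 174, and 174/0.9 = 194 after attrition. This agrees with the SAP. (Protocol 15.1.6 lists 45% for AAD; the same formula then gives 81 per arm, so 87 comes from 45.9%.)

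**2. Inputs.**
- From the documents: 105 per arm; 10% attrition; failure 100 − 69.9 = 30.1% (cryo) and 100 − 45 = 55% (AAD, Protocol; the SAP's figure gives 54.1%).
- Assumed, because the documents give no values: underlying HCU of 20-40%, equal in both arms; a fraction f of failures ablated later; every later ablation, crossover or repeat, counted as an HCU admission; timing uniform over days 91-365 and independent of other events.

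**3. Expected effect with no true difference.** At 12 months, P(event) = 1 − (1 − b)(1 − f × failure rate), with b the underlying risk. For b = 30%, ignoring dropout:

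| f | Ablated, AAD vs cryo | P(event), AAD vs cryo | Difference | SE (105 per arm) | Chance of z > 1.96 |
|---|---|---|---|---|---|
| 25% | 13.8% vs 7.5% | 39.6% vs 35.3% | 4.4 points | 6.7 | about 10% |
| 50% | 27.5% vs 15.1% | 49.3% vs 40.5% | 8.7 points | 6.8 | about 25% |
| 100% | 55% vs 30.1% | 68.5% vs 51.1% | 17.4 points | 6.7 | about 74% |

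The SE is √[(p₁q₁ + p₂q₂)/105]. The last column is the normal probability above 1.96 − difference/SE; for f = 50% that is 1.96 − 1.27 = 0.69.

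**4. Log-rank simulation with dropout, HCU.** Chance of a significant result favouring cryo at two-sided 0.05 (nominal 2.5%), over b = 20-40%:
- f = 25%: 8-11%
- f = 50%: 16-28%
- f = 75%: 33-52%
- f = 100%: 51-77%

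At the strictest Hochberg threshold (0.05/4 = 0.0125): 7-13% at f = 50% and 32-56% at f = 100%.

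**5. Cardioversion.** Assume that 10-30% of later ablations include a counted cardioversion and that the underlying risk is 5-20%. The chance is about 3-12% at f = 50% and 6-26% at f = 100%.

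**6. The other reading of the HCU 0.5-day sentence.** Let index stays count at 0.5 days for a share q of cryo subjects, with b = 30%. The test is significant *against* cryo in 43.9% (f = 50%) and 8.2% (f = 100%) of runs at q = 25%, in 99.9% and 94.5% at q = 50%, and in 100% at q = 100%.

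**7. One rule for both arms.** With events belonging to any ablation procedure left out in both arms, false results favouring cryo return to 2.3-2.7% (HCU) and 2.5-2.8% (cardioversion).

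**8. Internal conflict for cardioversion.** SAP 6.2.5.2.2 removes a cryo subject's cardioversion before index discharge, yet SAP 6.2.5.2.3 gives index-day cardioversions a survival time of 0.5 days without limiting the sentence to the AAD arm. The two agree only for a cryo subject discharged and then cardioverted on the same day.

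**The case against.** The strongest reply is that crossover follows failure of the assigned therapy, so its utilization is a real consequence of starting with drugs, and an as-randomized comparison should include it. That is a legitimate question. But a comparison of whole strategies would then count the index ablation as well, and a comparison of other utilization would count neither. The reply argues against replacing the HCU endpoint outright; it does not justify leaving the rule unstated.

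A reader might infer that both tests are positive by construction. The documents do not support that, for four reasons:
- No sentence says that the cryo index stay is excluded from HCU. The 0.5-day rule leaves it open, and the opposite reading reverses the bias.
- Repeat ablations in the cryo arm are foreseen and are not excluded, so they count on the same terms as crossovers. Ignoring them gives 66-93% at 30% crossover, which is too high a picture.
- Cardioversion at ablation is required only when sinus rhythm has not returned, so its inflation is modest unless crossover and procedural cardioversion are both frequent.
- Testing is gated on the primary objectives, and the Hochberg thresholds can be stricter than 0.05.

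Two further cautions stand. The documents do not define an HCU hospitalization or say that a planned ablation is one. And subjects who fail AAD therapy may already have had an HCU event, in which case a later crossover admission adds nothing to time to first event, so the independence assumption may overstate the inflation.

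On total versus first events, Protocol 15.3.3.5 does refer to the first HCU event, and the SAP summarizes HCU events by type and counts all cardioversions. The wording of the conclusion is loose; the test itself is clear.

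**Conclusion.** The concern holds in limited form. For cardioversion the difference between arms is explicit in the definition. For HCU it is the natural reading, but the text is incomplete, and the direction of the bias depends on a rule the plan does not state.

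On the natural reading, with cryo repeat ablations counted and the plan's failure rates, the false-positive chance in favour of cryo rises from 2.5% to roughly 8-11%, 16-28% or 51-77% for HCU as 25%, 50% or 100% of failures are ablated. For cardioversion it rises to about 3-12% at 50% and 6-26% at 100%. The crossover, HCU, admission and procedural-cardioversion rates behind these figures are assumptions, and the HCU figures may be too high for the reason given under the objection. The primary objectives are not affected. The change should be made before the data are analyzed.

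**What to change.** - **SAP 6.2.5.2.2** (and Protocol 15.3.4.2): apply one rule to both arms by excluding cardioversions before discharge from any study ablation, whether index, repeat or crossover. Bring the 0.5-day sentence in 6.2.5.2.3 into line with it.
- **SAP 6.2.5.1.2** (and Protocol 15.3.3.2): state one rule for both arms on whether index, repeat and crossover ablation stays are HCU events. Reconcile it with the 0.5-day sentence in 6.2.5.1.3.
- **Sensitivity analysis:** pre-specify the HCU comparison under the other rule. If ablation stays are included in the primary version, exclude all of them in both arms, and the reverse.
- **Conclusion:** word it as time to first event, not as a lower total rate. The planned descriptive summaries can carry the totals; no new model is needed.

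The cost is SAP text and a flag linking an admission or cardioversion to an ablation stay. Subsequent ablations already go on an eCRF (Protocol 11.5.6), and cardioversion use is collected at repeat and crossover procedures (Protocol 11.5.10). The downside for the sponsor is a possibly less favourable HCU and cardioversion contrast.

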##### **6.2.5.1.3. Analysis Methods**

The probability of a subject achieving freedom from HCU events (defined above) at 12 months will be estimated using Kaplan-Meier survival analysis. The standard error will be approximated using Greenwood's formula. A two-sided 95% log-log confidence interval for the probability at 12 months will be constructed. A two-sided log rank test will be used to assess whether the HCU event rate differs between treatment groups. If the p-value from this log-rank test is less than the alpha level determined by the Hochberg procedure (described in section 6.5), the objective will be considered met.

Day 0 is defined as day of the index cryoablation procedure or the day in which drug therapy is initiated. For subjects with treatment failure, the survival date will be set to the date of the first HCU event. For subjects without any HCU events through 12 months, those subjects will be censored at the last study contact date recorded on a CRF which may include the last study visit, the exit date or the date of death. If a subject without any HCU events is lost to follow-up, the censoring date will be set to the last known study visit date. For HCU events occurring on the day of index treatment, survival time will be set to 0.5 days.

The survival curve from 0 to 12 months will be presented for both treatment arms. HCU events will also be summarized by type and treatment group.

#### **6.2.5.1.4. Determination of Subjects for Analysis**

This analysis will be performed in the mITT dataset.

### **6.2.5.2. Cardioversions**

#### **6.2.5.2.1. Hypothesis**

The following hypothesis will be tested with a two-sided test.

$$H_0: \gamma_{\text{cryo}} = \gamma_{\text{AAD}}$$

$$H_a: \gamma_{\text{cryo}} \neq \gamma_{\text{AAD}}$$

where  $\gamma_{\text{cryo}}$  and  $\gamma_{\text{AAD}}$  are the 12-month rates of cardioversion (either electrical or pharmacological) in the cryoballoon ablation and AAD arms, respectively.

#### **6.2.5.2.2. Endpoint Definition**

A cardioversion event is defined as an electrical or pharmacological cardioversion post index ablation discharge for the treatment arm, and post AAD initiation for the AAD arm.

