11.5.3.9. Procedure Documentation

During the procedure the investigator will document the following:

- Catheters used (i.e. Arctic Front Advance™, Freezor® MAX and Achieve™ Mapping Catheter, etc.)
- Minimum temperature for each cryoapplication
- Duration of each cryoapplication
- Vein location for each cryoapplication (e.g. right superior PV)
- Use of phrenic nerve pacing or other phrenic nerve monitoring technique for each cryoapplication, specifically those cryoapplications surrounding the RS and RI PVs
- Demonstrated electrical block and, if real-time signals are available, time to isolation
- Adjunctive catheters, mapping or visualization devices, sedation type, procedure information, esophageal temperature, ACT, cardioversion use and fluoroscopy time will be collected.

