11.5.7. Cardioversions

Electrically and pharmacologically cardioverting the subject to sinus rhythm is allowed in the 90 day post-procedure blanking period (treatment arm)/AAD optimization period (control arm) at the discretion of the Investigator. Electrically or pharmacologically cardioverting the subject to sinus rhythm after the blanking period/AAD optimization period will be counted as an efficacy endpoint failure.

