15.3.4.2. Endpoint Definition

A cardioversion event is defined as an electrical or pharmacological cardioversion post index ablation discharge for the treatment arm, and post AAD initiation for the AAD arm

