15.3.4.3. Analysis Methods

The probability of a subject achieving freedom from cardioversion (defined above) at 12 months (365 days) will be estimated using Kaplan-Meier survival analysis. The standard error will be approximated using Greenwood's formula. A two-sided 95% log-log confidence interval for the probability at 12 months will be constructed. A two-sided log rank test, with significance level determined by the Hochberg procedure described above, will be used to assess whether the cardioversion rate differs between treatment groups.

Day 0 is defined as the day of the index cryoablation procedure or the day in which drug therapy is initiated. For subjects with at least one cardioversion, the survival date will be set to the date of the first cardioversion. For subjects without any cardioversions through 12 months, those subjects will be censored at the last study contact date recorded on a CRF which may include the last study visit, the exit date, or the date of death. If a subject without any cardioversions is lost to follow-up, the censoring date will be set to the last known study visit date. For cardioversions occurring on the day of index treatment, survival time will be set to 0.5 days.

The survival curve from 0 to 12 months will be presented for both treatment arms. Counts of all cardioversions administered over 12 months will also be summarized.

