15.3.4.5. Rationale for Performance Criteria

If the test specified above indicates a statistically significant increase in the time to the first cardioversion between cryoballoon ablation and AAD-treated subjects, this is sufficient evidence to say that the treatment has a lower rate of cardioversions within a year of treatment initiation, due to the randomized and intention-to-treat nature of the comparison.

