#### 6.2.2.2. Endpoint Definition

A treatment success is the opposite of a treatment failure.

A subject is considered a treatment failure if he/she experiences any of the following:

- Acute procedural failure (treatment arm only), which is any of these:
  - Inability to isolate all accessible targeted pulmonary veins (assessed for entrance block and, where assessable, exit block) during the index ablation procedure, OR
  - Left atrial non-PVI ablations including but not limited to, ablation of linear lesions, OR
  - Use of a non-study device in the left atrium.
- Documented AF/AT/AFL on ambulatory monitoring/12-lead ECG after the 90-day post-ablation blanking period (treatment arm).
  - Minimum of 30 seconds on ambulatory monitoring or 10 seconds on 12-lead ECG.
  - Note: Documented occurrence and treatment of typical right-sided cavotricuspid isthmus dependent atrial flutter is not considered a failure if confirmed by entrainment maneuvers during EP testing.
- Any subsequent AF surgery or ablation in the left atrium.
- Any subsequent cardioversion after the 90-day post-ablation blanking period.
- Class I or III antiarrhythmic drug (or sotalol) use after the 90-day blanking period (treatment arm only).

The blanking period is defined as the first 90 days after the index ablation procedure (treatment arm) or AAD initiation (control arm). Recurrences of atrial arrhythmias during the blanking period will not be counted in the determination of the first clinical failure for the primary endpoint. Within the 90-day blanking period, recurrent arrhythmias can be managed with medications or cardioversions.

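### Cardioversions count from discharge in the cryo arm but from drug start in the AAD arm; taken alone, this can shift the secondary test only towards cryo or not at all, by an amount the documents do not fix

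*SAP*

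**What the plan says.** The comparison is one of two hypotheses under secondary objective 2.

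- **Event.** Protocol 15.3.4.2: "A cardioversion event is defined as an electrical or pharmacological cardioversion post index ablation discharge for the treatment arm". In the control arm counting begins at drug start. SAP 6.2.5.2.2 has the same rule: "cardioversion post index ablation discharge for the treatment arm, and post AAD initiation for the AAD arm".
- **Clock.** Protocol 15.3.4.3, repeated in SAP 6.2.5.2.3: "Day 0 is defined as the day of the index cryoablation procedure or the day in which drug therapy is initiated". Time to first cardioversion is compared by a two-sided log-rank test in the mITT set. A cardioversion on the day of index treatment is given a time of 0.5 days, with no arm named.
- **Cardioversion around treatment.** Protocol 11.5.3.8, for subjects not yet back in sinus rhythm: "Electrical or pharmacological cardioversion to sinus rhythm must be attempted following the PVI portion of the procedure". Afterwards, under Protocol 11.5.7, cardioversion is "allowed in the 90 day post-procedure blanking period (treatment arm)/AAD optimization period (control arm) at the discretion of the Investigator".
- **Inference.** On a significant result, Protocol 15.3.4.5 states: "this is sufficient evidence to say that the treatment has a lower rate of cardioversions within a year of treatment initiation".
- **Error control.** SAP 6.5 tests this as one of four Hochberg hypotheses, only if the primary objectives are met. The level for a single hypothesis runs from 0.0125 (0.05/4) to 0.05.

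Other endpoints start at matched points. Health care utilization events count from index ablation or therapy initiation (SAP 6.2.5.1.2), and the primary efficacy blanking period is 90 days in each arm (SAP 6.2.2.2).

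**The concern.** From day 0 to discharge, cryo subjects are in the risk set but no cardioversion of theirs can count. AAD subjects over the same days are also in the risk set, and theirs do count. Leaving out cardioversion at the index procedure is defensible, because the protocol itself calls for it. The defect is that the AAD arm has no corresponding start.

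At stake is a hypothesis-tested secondary claim. Randomization and analysis as randomized, on which Protocol 15.3.4.5 relies, do not protect a comparison whose counting windows differ by arm. The cryo count also leaves out the days right after treatment initiation, so the claimed period is not the one counted. Discharge, moreover, is not a fixed time: a longer index stay gives a longer interval in which nothing counts.

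**Working it through.** **The plan's figures.** Neither document gives a sample size, event rate or power for cardioversion. The only usable figure is the trial size, set by the safety objective in SAP 7.2. With n = 94 and success at 5 or fewer events, P(X ≤ 5 | 12%) = 0.0246 and P(X ≤ 5 | 4%) = 0.825. Then 94/0.90 = 104.4, rounded up to 105 per arm and 210 in total. All of these match the SAP.

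**Direction.** With 105 per arm at risk, each early event counted only in the AAD arm adds 1 − 105/210 = 0.5 to that arm's observed-minus-expected total. Take 10% later risk in both arms (about 21 later events) and a 5% early AAD share (5.25 events). The shift in z is about 5.25 × 0.5 / √[(21 + 5.25)/4] = 2.625/2.56 = 1.02 towards cryo. Simulation of that case gave a mean z of −1.02 as planned (negative favours cryo) and 0.00 with a matched later start. Across 10 scenarios, with and without frailty, mean z always moved towards cryo against both matched starts. Within single data sets the planned rule was never less favourable to cryo than a day-0 count. It was less favourable than the matched later start in at most 0.5% of data sets, in one extreme scenario.

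**What drives it.** Only early AAD events do. With none, and 20% uncounted procedural cardioversions in the cryo arm, rejection was 3.9% (2.2% favouring cryo), so there was no inflation.

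**Plausible early share.** The documents give neither an early AAD cardioversion rate nor a length of stay. Under a constant hazard with 12-month rate p, the share in w days is 1 − (1 − p)^(w/365). That is 0.014% for p = 5%, w = 1, and 0.236% for p = 25%, w = 3.

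**Type I error.** Log-rank simulation with 20,000 replicates, 105 per arm, equal later 12-month rates of 5, 10, 15 or 25%, 10% dropout, and an illustrative matched time of day 3. All rates are assumed. Ranges are over the four later rates.

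| Early AAD share | Two-sided 0.05 | Two-sided 0.0125 | One-sided 0.025, favouring cryo |
|---|---|---|---|
| 0% | 4.7-4.9% | 0.9-1.2% | 2.3-2.5% |
| 0.3% | 4.7-5.2% | 1.0-1.3% | 2.8-3.1% |
| 1% | 5.2-5.6% | 1.2-1.4% | 3.5-4.5% |
| 2% | 5.9-8.7% | 1.4-2.4% | 4.6-8.2% |
| 3% | 7.2-13.4% | 2.0-4.4% | 6.3-13.2% |
| Common fixed-day start | 4.6-5.3% | 0.9-1.3% | 2.2-2.8% |

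A separate simulation (1,500 runs per cell) agrees: at 2% early events, two-sided error was 7.7% (10% later risk) and 6.5% (20%).

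**Shift in the 12-month difference.** Early share × (1 − later rate). At 1%: 0.01 × 0.75 to 0.01 × 0.95, or about 0.8-1.0 points. At 3%: 0.03 × 0.75 to 0.03 × 0.95, or about 2.3-2.9 points.

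**The case against.** The strongest reply is that counting starts in each arm once the assigned treatment has been delivered: a hospital procedure in one, starting a drug in the other. Arm-specific rules are deliberate elsewhere; acute procedural failure, for instance, counts only in the treatment arm. The window is also short. Reaching 2% in three days needs about 2/0.236 = 8 times the later hazard at a 25% rate, or 2/0.042 = 48 times at a 5% rate, and no passage documents such clustering.

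Much of this stands. At a flat hazard the effect is negligible. Early events are possible, since cardioversion is allowed from drug start and pharmacological conversion counts, but that shows plausibility and not frequency. The reply does not explain why the AAD arm lacks a matching start.

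A reader might go further in three ways that the documents do not support.

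- *The whole test can only be biased towards cryo.* That describes this definition alone. SAP 6.2.4 expects many AAD subjects to cross over and says this biases an intention-to-treat comparison towards the null. It says so about quality of life, but cardioversion is also analysed as randomized.
- *The error is severely inflated.* Early shares of 5% and 10% give 11-28% and 30-69% two-sided rejection, but these are stress tests with no support in the documents.
- *Counting from day 0 in both arms is the cure.* It is not neutral, because procedural cardioversion is required. With assumed early rates of 20% cryo and 1% AAD, and equal later risk (10%), it rejects 92% of the time, never in favour of cryo.

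Blocks next to both analysis sections are redacted, so a supporting analysis there cannot be ruled out; none is visible.

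**Conclusion.** The point holds in limited form. The counting windows differ by arm on a shared clock, and this feature alone pushes towards cryo or has no effect. Its size is unknown. Up to about 1% early AAD events the two-sided error is close to nominal, although at 1% the errors already fall mostly on the cryo side. At an assumed 2-3%, it is about 6-13% at the 0.05 level and 1.4-4.4% at the strictest Hochberg level of 0.0125. These figures rest on assumed event rates, equal later risk and 105 subjects per arm.

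Whatever the size, the period claimed in Protocol 15.3.4.5 does not match what is counted in the cryo arm. The planned summary of all cardioversion counts is descriptive and does not change the test. The consequence is confined to one of four secondary hypotheses. The change should be made; confidence in its practical importance is medium.

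**What to change.** In SAP 6.2.5.2.2-6.2.5.2.3 and Protocol 15.3.4.2-15.3.4.3, start both event counting and the survival clock for this test at one fixed study day after index treatment or AAD initiation. Use the same day in both arms, set it before the data are analysed, choose it to cover the usual index stay, and apply it whatever the actual discharge date. Subjects with an earlier cardioversion stay at risk, so the endpoint becomes first cardioversion after that day. Reword Protocol 15.3.4.5 to match.

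Report cardioversions before that day descriptively by arm, with cryo index-procedure cardioversions shown separately. Present any day-0 count as descriptive or sensitivity only, noting that it is weighted against cryo because of Protocol 11.5.3.8.

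No new data are needed. The analysis already uses cardioversion dates, and for the procedure Protocol 11.5.3.9 says "cardioversion use and fluoroscopy time will be collected". The costs are:

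- Early AAD events, and cryo events between discharge and the fixed day, leave the test. For a stay beyond the fixed day, later in-hospital cryo events would enter it.
- Power falls, although the part lost came from the unequal window. For later rates of 5% against 15%, power at 0.05 goes from 70% to 68% with 0.3% early events, 74% to 68% with 1%, and 84% to 67% with 3%. For 10% against 25%, it goes from 82% to 81%, 85% to 81%, and 90% to 81%.
- A protocol and SAP amendment is needed, with the approvals listed in Protocol 17.6.
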